#### **7.2.2. Clinical Laboratory Safety Analyses**

Laboratory evaluations including the analyses of chemistry laboratory tests, hematology laboratory tests and urinalysis will be based on GSK Core Data Standards.

Haematology, clinical chemistry and urinalysis parameters collected are listed below.

### Protocol Required Safety Laboratory Assessments

Laboratory Assessments	Parameters			
Hematology	Platelet Count	RBC Indices: MCV MCH %Reticulocytes		WBC count with Differential : Neutrophils Lymphocytes Monocytes Eosinophils Basophils
	RBC Count			
	Hemoglobin			
	Hematocrit			
Clinical Chemistry	BUN	Potassium	Aspartate Aminotransferase (AST)/ Serum Glutamic-Oxaloacetic Transaminase (SGOT)	Total bilirubin
	Creatinine	Sodium, Chloride, Bicarb	Alanine Aminotransferase (ALT)/ Serum Glutamic-Pyruvic Transaminase (SGPT)	Total Protein
	Glucose (non-fasting)	Calcium, Magnesium, Phosphate	Alkaline phosphatase	Fasting Lipid Panel (Cholesterol, Triglycerides, HDL, LDL)
Routine Urinalysis	
 
• Specific gravity
 
• pH, glucose, protein, blood, ketones, bilirubin, urobilinogen, nitrite, leukocyte esterase by dipstick
 
• Microscopic examination (if blood or protein is abnormal)
 
			

The following summaries will be provided:

- Laboratory values for hematology, clinical chemistry, and urinalysis by visit and by treatment
- Laboratory values change from baseline for hematology and clinical chemistry by visit and by treatment group
- The number and percentage of subjects with on-treatment laboratory abnormalities worsened from baseline by maximum grade for haematology, clinical chemistry and urinalysis.
- Treatment emergent laboratory toxicities

The following listings will be provided:

- Laboratory values for haematology, clinical chemistry, and urinalysis
- Laboratory values of potential clinical importance for hematology, clinical chemistry and urinalysis (potential clinical importance criteria are specified in Section 12.8.1)
- Laboratory results identified as adverse events
- Subjects with grades 2 or higher laboratory toxicities

### **7.2.3. Other Safety Analyses**

#### **7.2.3.1. Electrocardiograms**

A summary of the number and percentage of subjects of all ECG findings will be displayed by treatment. Additionally, summary statistics of ECG values and change from baseline in ECG values will be presented. Maximum QTc values and maximum increase in QTc values post-baseline relate to baseline will be summarized by category. Mean (95% CI) change from baseline in QTcF interval will be plotted by time and treatment. A by-subject listing of ECG findings for all subjects will be listed. Abnormal ECG findings and all ECG values for subjects with a value of potential clinical importance will be listed (potential clinical importance criteria are specified in Section 12.8.2).

#### **7.2.3.2. Vital Signs**

Vital sign values and change from baseline will be summarized. A by-subject listing of vital signs for all subjects will be produced. All vital signs for subjects with values of potential clinical importance will be listed (potential clinical importance criteria are specified in Section 12.8.3)

#### **7.2.3.3. Hepatobiliary (Liver)**

Liver monitoring/stopping event reporting will be summarized by treatment group. A summary of hepatobiliary laboratory abnormalities will be produced.

## 8. PHARMACOKINETIC ANALYSES

### 8.1. Pharmacokinetic Analyses

The pharmacokinetic (PK) analyses will be based on the “PK Concentration” and “PK Parameter” population, unless otherwise specified.

As an overview, individual, mean and median plasma GSK3640254 concentration-time profiles will be plotted by treatment and day (linear and semi-linear profiles). PK sampling times will be related to the start of the dosing date/time. Actual sampling times will be used to calculate all of the non-compartmental pharmacokinetic parameters. Individual concentrations of GSK3640254 in plasma will be listed and summarised by treatment and nominal time. Details of the planned displays are presented in Appendix 12: List of Data Displays.

Table 3 provides an overview of the planned analyses, with full details being presented in Appendix 12.

**Table 3 Overview of Planned Pharmacokinetic Analyses**

Display Type	Untransformed							Log-Transformed						
	Stats Analysis			Summary		Individual		Stats Analysis			Summary		Individual	
	T	F	L	T	F	F	L	T	F	L	T	F	F	L
PK Concentrations														
Plasma Drug Concentrations				Y	Y	Y	Y					Y	Y	
PK Parameters														
PK Parameters				Y	Y	Y	Y	Y	Y	Y	Y	Y	Y	

**NOTES :**

- T = Table, F = Figure, L = Listings, Y = Display generated.
- Stats Analysis = Represents TFL related to any formal statistical analyses (i.e. modelling) conducted.
- Summary = Represents TFL related to any summaries (i.e. descriptive statistics) of the observed raw data.
- Individual = Represents FL related to any displays of individual subject observed raw data.

#### 8.1.1. Endpoint / Variables

##### 8.1.1.1. Drug Concentration Measures

Refer to Appendix 5: Data Display Standards & Handling Conventions (Section 12.5.3 Reporting Standards for Pharmacokinetic)

##### 8.1.1.2. Derived Pharmacokinetic Parameters

Pharmacokinetic parameters will be calculated by standard non-compartmental analysis according to current working practices and using the currently supported version of WinNonlin. All calculations of non-compartmental parameters will be based on actual sampling times. Pharmacokinetic parameters listed will be determined from the plasma concentration-time data, as data permits.

Parameter	Parameter Description
-----------	-----------------------

AUC(0-inf)	Area under the concentration-time curve extrapolated to infinity will be calculated as: AUC = AUC(0-t) + C(t) / <math>\lambda_z</math>
AUC(0-tlast)	Area under the concentration-time curve from time zero to the time of the last quantifiable concentration (C(t)) will be calculated using the linear trapezoidal rule for each incremental trapezoid and the log trapezoidal rule for each decremental trapezoid.
AUC(0-24)	Area under the plasma concentration time curve from zero to 24
AUC(0- $\tau$ )	Area under the curve (Area under the plasma drug concentration-time curve from pre-dose to the end of the dosing interval at steady state)
%AUC ex	The percentage of AUC (0-inf) obtained by extrapolation (%AUC ex ) will be calculated as: [AUC(0-inf) – AUC(0-t)] / AUC(0-inf) x 100
C max	Maximum observed concentration, determined directly from the concentration-time data.
C 24	Concentration at 24 hours post-dose on Day 1
C last	Last quantifiable concentration
C <math>\tau</math>	Pre-dose (trough) concentration at the end of the dosing interval
t max	Time to reach C max , determined directly from the concentration-time data.
t 1/2	Apparent terminal half-life will be calculated as: t1/2 = ln2 / <math>\lambda_z</math>
t lag	Absorption lag time
t last	Time of last quantifiable concentration
CL/F	Apparent oral clearance

**NOTES:**

- Additional parameters may be included as required.

**8.1.2. Summary Measure**

- Part 1 (single dose): AUC (0-24), AUC(0-tlast), AUC (0-inf), Cmax, C24, tmax, tlag, t1/2, Clast, tlast, CL/F.
- Part 2 (Repeated QD doses for 14 days):
  - Day 1: AUC(0-24), Cmax, C24, tmax, tlag
  - Day 14: AUC(0- $\tau$ ), Cmax, C $\tau$ , tmax, t1/2, and CL/F.

**8.1.3. Population of Interest**

The primary pharmacokinetic analyses will be based on the Pharmacokinetic Parameter population, unless otherwise specified.

**8.1.4. Statistical Analyses / Methods**

Details of the planned displays are provided in Appendix 12: List of Data Displays and will be based on GSK Data Standards and statistical principles.

Unless otherwise specified, endpoints / variables defined in Section 8.1.1 will be summarised using descriptive statistics, graphically presented (where appropriate) and listed.

### 8.1.4.1. Statistical Methodology Specification

#### Dose Proportionality-Power model:

*Part 1, and 2:*

Dose proportionality of GSK3640254 following single-dose administration in Part 1 and following single-dose and repeat-dose administration in Part 2 of the study will be assessed separately using the power model (Smith, 2000) as described below:

$$y = \alpha * dose^{\beta}$$

where y denotes the PK parameter being analyzed [for Part 1: AUC(0-∞), AUC(0-24), and Cmax. For Part 2: AUC(0-24), Cmax on Day1;

AUC(0-τ), Cmax, Cτ on Day 14] . Dose proportionality implies that β=1 and will be assessed by estimating β along with its confidence interval. The exponent, β, in the power model will be estimated by regressing the loge-transformed PK parameter on loge dose.

$$\log(y) = \log(\alpha) + \beta * \log(\text{dose})$$

The power model will be fitted by restricted maximum likelihood (REML) using SAS

Proc Mixed. For Part 1, a power model with subject as the random effect will be fitted. If the model does not converge then a fixed effect power model will be fitted. For Part 2, a fixed effect power model will be fitted. The mean slope will be estimated from the power model and the corresponding 90% confidence interval calculated. Intra-subject CV% calculated from the model will be presented in the table. Point estimates and confidence intervals for the slope will be reported to 4 decimal places with no rounding.

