Preliminary PK parameters on Day 1 and Day 14 for GSK3640254 following repeat dose administration of 50, 100 and 200 mg for 14 days are summarized in [Table 4](#). The exposures on Day 14 are on average 2-3 folds higher than that on Day 1. Cmax and AUC on Day 14 tended to increase in a close to dose proportional manner from 50 to 200 mg. The maximum observed mean Cmax for the repeat dose administration is 1528 ng/mL at the dose of 200 mg on Day 14. The maximum observed mean AUC(0-24) for the repeat dose administration is 23046 ng.hr/mL at the dose of 200 mg on Day 14.

The anticipated mean Cmax at a proposed dose of 320 mg based on the observed exposures ([Table 4](#)) using a dose proportionality model is predicted to be 1030 ng/mL on Day 1 and 2475 ng/mL for Day 14. The anticipated mean AUC(0-24) on Day 14 at a proposed dose of 320 mg based on observed exposures ([Table 4](#)) using a dose proportionality model is predicted to be 37942 ng.hr/mL. The probability of any subject exceeding the PK stopping criteria for MAD study with the dose of 320 mg repeat dosing, which is AUC(0-24) of 61100 ng.hr/mL based on LOAEL exposure in rat at 30 mg/kg, is 42% based on data collected through 9th May. The probability of any subject exceeding the PK stopping criteria for SAD study with the dose of 320 mg repeat dosing, which is a Cmax of 7960 ng/mL based on minimal QT effects observed in one dog, is 0.7% based on data collected through 9th May.

Table 4 Summary of Preliminary PK Parameters Following Repeat Dose administration of GSK3640254 in study 207187

PK Parameter	Day 1			Day 14		
	Dose			Dose		
	50 mg	100 mg	200 mg	50 mg	100 mg	200 mg
	Geometric Mean (CV%) [N]*					
AUC (0-24)	2867.4 (30) [6]	6826.2 (23) [6]	8947.1 (49) [NP]	6285.6 (34) [6]	17537.5 (14) [6]	23046.2 (36) [NP]
C _{max}	214.5 (24) [6]	535.6 (23) [6]	689.2 (40) [NP]	413.5 (32) [6]	1182 (10) [6]	1528.4 (30) [NP]
T _{1/2(z)}	NC	NC	NC	24.5 (8) [6]	28.6 (19) [6]	21.9 (12) [NP]
T _{max}	3.8 (3-5) [6]	4.3 (2-5) [6]	4 (1.5- 5.5) [NP]	3.8 (2.5-5) [6]	4 (1.5-4.5) [6]	3.5 (2-5) [NP]
* T _{max} has been reported as Median (Min - Max)						
Units: C _{max} in ng/mL, AUC in ng.h/mL and T _{max} in hours						
NP: Not Printed as the expansion cohort is still running. This includes 6 active subjects from Cohort 5 and the subjects from expansion cohort 7 studied thru May 9 th , 2018.						
NC: Not Computed						

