## **Part 2,**

*ODS output solutionf=stat*

*Proc Mixed;*

*model logPKvar = logdose /cl alpha=0.1 solution ddfm=kr;*

*run;*

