## **Dose Proportionality-ANOVA Model**

*Part 1, and 2:*

Additionally, dose proportionality may be assessed by pair-wise analysis of variance (ANOVA) using the SAS Mixed model procedure if power model does not show dose proportionality. A reference dose of 3 mg for all parts, and will be used and the other doses would be treated as test dose. PK parameters will be normalized to the reference dose and then log-transformed prior to the analysis. Point estimates and 90% confidence intervals for AUC and Cmax will be reported to 4 decimal places with no rounding. An example of SAS code is also included here for the ANOVA approach.

*ODS output solutionf=stat;*

*Proc Mixed;*

*class treatment; /\* treatments are different dose groups \*/*

*model logdnPKvar = treatment/ddfm=kr;*

*lsmeans treatment; /\* assuming one ref and four test treatments \*/*

*estimate 'test1 vs ref' treatment -1 1 0 0 0 /cl alpha=0.1;*

*estimate 'test2 vs ref' treatment -1 0 1 0 0 /cl alpha=0.1;*

*run;*

Individual and box plot of dose-normalized plasma GSK3640254 PK parameters by treatment will be generated.

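### Part 2 dose proportionality rests on one power-model slope with no check of fit, and the per-dose comparison that could back it up is optional, loosely triggered and tied to a 3 mg reference outside Part 2

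*SAP*

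**What the plan says.** SAP 8.1.4.1 sets the criterion: "Dose proportionality implies that β=1 and will be assessed by estimating β along with its confidence interval". On the interval it adds "The mean slope will be estimated from the power model and the corresponding 90% confidence interval calculated". For Part 2 the model is "For Part 2, a fixed effect power model will be fitted", and the sample code has log dose as its only term: "model logPKvar = logdose /cl alpha=0.1 solution ddfm=kr". The section gives no curvature term, lack-of-fit statistic, acceptance range or rule for reading the interval.

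The ANOVA subsection says that pairwise comparison may be done "using the SAS Mixed model procedure if power model does not show dose proportionality". It does not define that condition. On the reference it says "A reference dose of 3 mg for all parts, and will be used and the other doses would be treated as test dose". SAP 2.3 gives the Part 2 doses as 50, 100, 200 and 320 mg.

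Two items are not conditional. The same subsection plans individual and box plots of dose-normalised parameters. Appendix 12 lists Tables 4.11 and 4.12 (Part 2 ANOVA, Day 1 and Day 14) as deliverables with no condition attached, in conflict with the optional wording of the text.

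Protocol 3.2.2 already describes the Day 14 exposures in Table 4 as having "tended to increase in a close to dose proportional manner from 50 to 200 mg".

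**The concern.** Dose proportionality after repeated dosing is a secondary objective, with Day 14 AUC(0-τ), Cmax and Cτ as its endpoints. One slope averages over the dose range. If exposure rises too steeply over one step and too little over the next, the slope can sit near 1 although neither step is proportional, and its interval says nothing about that misfit because it takes the line as correct. Part 2 is exposed to this because each dose comes from its own cohort, so a shift in one cohort appears as a departure from the line. The per-dose comparison would show the pattern. In the text it is triggered only by the slope, and its stated reference dose was never given in Part 2.

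**Working it through.** **Inputs** (Protocol 3.2.2, Table 4, Day 14; geometric mean, CV%, n at 50 / 100 / 200 mg):
- AUC(0-24): 6285.6 (34%, 6); 17537.5 (14%, 6); 23046.2 (36%, not printed)
- Cmax: 413.5 (32%, 6); 1182 (10%, 6); 1528.4 (30%, not printed)

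Assumptions: CV% is geometric, so the log-scale variance is ln(1+CV²). The 200 mg n is varied from 6 (Cohort 5 only) to 24 (Cohort 5 plus 18 expansion actives).

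**Reproducing the protocol's figures.** Protocol 3.2.2 predicts 320 mg means of 1030 (Day 1 Cmax), 2475 (Day 14 Cmax) and 37942 (Day 14 AUC). A power model fitted to Table 4 with n = 14 at 200 mg gives 1054, 2464 and 36987, that is +2.3%, −0.4% and −2.5%. A strict slope of 1 through the three doses gives 1374, 2904 and 43664. The reconstruction is therefore close, and the protocol's predictions fit a power model with a slope below 1.

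**Steps per dose doubling, Day 14.**
- AUC: 17537.5/6285.6 = 2.79; 23046.2/17537.5 = 1.31. Dose-normalised: 2.79/2 = 1.40 and 1.31/2 = 0.66.
- Cmax: 1182/413.5 = 2.86; 1528.4/1182 = 1.29. Dose-normalised: 1.43 and 0.65.

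**Slope and fit.** Weighted regression of log geometric mean on log dose. Residual variance = (SS pure error + SS lack of fit)/(N−2). Lack-of-fit F = SS lack of fit / [SS pure error/(N−3)].

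AUC with n = 24 at 200 mg (N = 36):
- SS pure error = 5(0.1094) + 5(0.0194) + 23(0.1219) = 3.447; SS lack of fit = 0.648; Sxx = 10.09
- s² = (3.447 + 0.648)/34 = 0.1204; SE = √(0.1204/10.09) = 0.109; t = 1.691
- Slope 0.860, 90% CI 0.675 to 1.044
- F = 0.648/(3.447/33) = 6.20, p = 0.018

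| Day 14 | n at 200 mg | Slope (90% CI) | Lack-of-fit p |
|---|---|---|---|
| AUC | 6 | 0.937 (0.692–1.182) | 0.020 |
| AUC | 12 | 0.888 (0.678–1.098) | 0.018 |
| AUC | 24 | 0.860 (0.675–1.044) | 0.018 |
| Cmax | 6 | 0.943 (0.713–1.173) | 0.007 |
| Cmax | 12 | 0.891 (0.699–1.083) | 0.005 |
| Cmax | 24 | 0.861 (0.697–1.026) | 0.004 |

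The observed 100 mg geometric mean lies 29% to 35% above the fitted line across these cases. Dose-normalised ratios (90% CI) at n = 24:
- AUC: 100/50 mg 1.40 (1.02–1.91); 200/100 mg 0.66 (0.51–0.84)
- Cmax: 100/50 mg 1.43 (1.09–1.87); 200/100 mg 0.65 (0.52–0.80)

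**Day 1.** At n = 24 the slopes are 0.759 (0.535–0.984) for AUC and 0.774 (0.581–0.966) for Cmax. The interval excludes 1 from n = 14 (Cmax) and n = 18 (AUC).

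**Adding 320 mg, Day 14** (assumed: 320 mg n = 6 and CV 35%; 200 mg n = 24 at the Table 4 mean):
- 320/200 ratio 1.4: AUC slope 0.827 (0.670–0.985), Cmax 0.828 (0.686–0.971). Both exclude 1.
- Ratio 1.6: AUC 0.869 (0.712–1.026), Cmax 0.870 (0.728–1.011). Both include 1.
- The protocol's own predictions (37942/23046.2 = 1.65; 2475/1528.4 = 1.62): AUC 0.878 (0.721–1.035), Cmax 0.874 (0.732–1.015). Both include 1, with lack-of-fit p 0.056 and 0.018.

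**Cohort check.** The protocol's amendment summary gives Cohort 5 alone a mean Day 14 Cmax of 1841, against 1528 pooled with the expansion participants then studied. The 100 to 200 mg step becomes 1841/1182 = 1.56. With n = 6 and an assumed CV of 20% to 40%, lack-of-fit p is 0.015 to 0.055.

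**The case against.** A reader might infer that the SAP, followed as written, would report Part 2 as dose proportional and give no per-dose results. The documents do not support that.

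- Tables 4.11 and 4.12 and the dose-normalised plots are listed without condition, and geometric means are summarised by treatment. A rise and then a fall in dose-normalised exposure would be visible somewhere in the output.
- No rule says that an interval containing 1 means proportional. That step would be the reader's own.
- Table 4 is preliminary. The final fit adds 320 mg and the complete 200 mg group, and the slope itself would exclude 1 if 320 mg exposure is about 1.4 times the 200 mg exposure or less.
- Day 1 is also a Part 2 analysis, and there the slope departs from 1 once the 200 mg group is large enough.
- Part of the misfit may be a difference between cohorts, which no fit test can separate from non-proportionality.
- SAP 2.4 plans no statistical testing, so a significance test that gates the conclusion would sit badly with it.

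All of this stands, and it limits the consequence. It does not supply a working per-dose analysis. The text and the display list disagree on whether the ANOVA is run, and with 3 mg as the reference it cannot be run for Part 2 as specified. The plots carry no ratio or interval.

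**Conclusion.** The point holds as a weakness in how Day 14 proportionality will be read. On the preliminary data, opposite departures of about +40% and −35% in dose-normalised exposure leave a slope of 0.86 to 0.94 with 1 inside the 90% CI for every 200 mg n tried, while lack of fit is p about 0.02 for AUC and 0.004 to 0.007 for Cmax. The slope alone could mask this. Whether it does in the final four-dose analysis is open: under the stated 320 mg assumptions the interval excludes 1 at a 320/200 ratio of 1.4 and includes it at 1.6, and it includes it at the protocol's own predictions. Day 1 is less affected. These figures rest on geometric CVs, on an unprinted 200 mg n, and on pooling two cohorts whose Cmax appears to differ. The p-values here describe misfit and are not proposed as a decision rule.

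**What to change.** In SAP 8.1.4.1, for Part 2:

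1. Always report adjacent-dose, dose-normalised geometric mean ratios with 90% CIs (100/50, 200/100 and 320/200 mg) in Tables 4.11 and 4.12. This replaces the 3 mg reference and the optional, conditional wording, and brings the text into line with Appendix 12.
2. Report a descriptive fit check beside the slope (dose as a class variable, or a quadratic log-dose term). State that the slope is read together with the per-dose ratios, not through a significance gate.
3. Show Cohort 5 and the Expansion Cohort separately at 200 mg as well as pooled, as a same-dose view of cohort shift.

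Cost: a few lines of SAP text and SAS code, and no new data. The fit check has low power at 6 per dose, so an unremarkable result is not evidence of fit, and it cannot tell a cohort shift from non-proportionality. The proportionality statement may become less favourable.

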#### **Part 1,**

*An example of SAS code is included here for the power model approach.*

*ODS output solutionf=stat*

*Proc Mixed;*

*class subject;*

*model logPKvar = logdose /cl alpha=0.1 solution ddfm=kr;*

*random intercept /subject=subject type=un;*

*run;*

*If the above model still does not converge, then use:*

*ODS output solutionf=stat*

*Proc Mixed;*

*model logPKvar = logdose /cl alpha=0.1 solution ddfm=kr;*

*run;*

## **Part 2,**

*ODS output solutionf=stat*

*Proc Mixed;*

*model logPKvar = logdose /cl alpha=0.1 solution ddfm=kr;*

*run;*

## **Dose Proportionality-ANOVA Model**

*Part 1, and 2:*

Additionally, dose proportionality may be assessed by pair-wise analysis of variance (ANOVA) using the SAS Mixed model procedure if power model does not show dose proportionality. A reference dose of 3 mg for all parts, and will be used and the other doses would be treated as test dose. PK parameters will be normalized to the reference dose and then log-transformed prior to the analysis. Point estimates and 90% confidence intervals for AUC and Cmax will be reported to 4 decimal places with no rounding. An example of SAS code is also included here for the ANOVA approach.

*ODS output solutionf=stat;*

*Proc Mixed;*

*class treatment; /\* treatments are different dose groups \*/*

*model logdnPKvar = treatment/ddfm=kr;*

*lsmeans treatment; /\* assuming one ref and four test treatments \*/*

*estimate 'test1 vs ref' treatment -1 1 0 0 0 /cl alpha=0.1;*

*estimate 'test2 vs ref' treatment -1 0 1 0 0 /cl alpha=0.1;*

*run;*

Individual and box plot of dose-normalized plasma GSK3640254 PK parameters by treatment will be generated.

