		50 mg	100 mg	200 mg
Ear and Labyrinth Disorders	Ear Discomfort			1
	Excessive Cerumen Production			1
Renal and Urinary Disorders	Pollakiuria			1
	Dysuria			1
Respiratory, Thoracic, and Mediastinal Disorders	Epistaxis	1		
	Transaminases Increased	1		
Cardiac Disorders	Palpitations			1
Total AEs by Blinded MAD Cohort/Period		19	17	43

Preliminary PK parameters for GSK3640254 following single dose administration from 1 to 700 mg are summarized in [Table 3](#). GSK3640254 is slowly absorbed with maximum concentration observed on average 3-4 hours after dosing and slowly eliminated with an average half-life of 24 hours. C_{max} and AUC increased in a close to dose proportional manner from 1 to 400 mg with a plateauing in exposure at the 700 mg dose. The maximum observed mean C_{max} for the single dose administration ([Table 3](#)) is 1881 ng/mL at the dose of 400 mg. The maximum observed mean AUC(0-inf) for the single dose administration ([Table 3](#)) is 43116 ng.hr/mL at the dose of 400 mg. The mean exposure observed at 700 mg is slightly lower than that at 400 mg single administration and thus we anticipate similar exposures with doses greater than 700 mg.

Table 3 Summary of Preliminary PK Parameters Following Single Doses of GSK3640254 in study 207187

PK Parameter	Dose							
	1 mg	3 mg	10 mg	30 mg	100 mg	200 mg	400 mg	700 mg
	Geometric Mean (CV%) [N]*							
Cmax	4.9 (16) [6]	13.8 (31) [6]	47 (30) [6]	129.8 (21) [6]	372.1 (72) [6]	578.9 (27) [6]	1881 (50) [6]	1760.8 (44) [6]
Tmax	3.5 (2.5-6) [6]	4.5 (2-5) [6]	3.5 (2.5-5) [6]	4 (2.5-5) [6]	3.8 (2-5) [6]	3 (2-4) [6]	3.3 (2-6) [6]	3.3 (2-4.5) [6]
T1/2(z)	NC	22 (14) [6]	25.8 (17) [6]	23.3 (16) [6]	23.9 (14) [6]	23.2 (17) [6]	23.3 (16) [6]	22.2 (28) [6]
AUC	NC	340 (29) [6]	1229.3 (19) [6]	3008 (26) [6]	8566.4 (67) [6]	14978 (41) [6]	43115.7 (52) [6]	39972.5 (50) [6]
* Tmax has been reported as Median (Min - Max)								
AUC represents AUC(0-inf); NC: Not Computed								
Units: Cmax in ng/mL, AUC in ng.h/mL, t1/2 and tmax in hours								

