5.5.2. Predicted Human Effective Dose

Steady-state trough concentrations are typically the PK parameter of interest for efficacy for other antiretroviral classes such as protease inhibitors and integrase inhibitors. The minimum target steady state trough level for GSK3640254 was established using a value of 3 times the protein binding-adjusted EC₉₀ (3xPBA-EC₉₀) for one of the least sensitive variants, a triple-mutant polymorph (R361K/V362I/L363M), from a library of 36 gag/pr genotyped viruses. This virus exhibited EC₅₀, EC₉₀ and 3x PBA EC₉₀ values of 3, 7 and 150 nM (0.11 µg/mL), respectively. This 3xPBA-EC₉₀ represents the anticipated minimal effective trough concentration of GSK3640254.

The potential minimally effective dose for GSK3640254 was initially estimated using the predicted human PK profile, assuming similar between-participant PK variability to that observed with GSK3532795 (Population PK model based on data from Phase 2b study AI468038, [Metrum Research Group](#), 2016), to ensure that 95% of participants have steady state trough concentrations that exceed the target concentration of 0.11 µg/mL following once daily dosing of GSK3640254. This led to the prediction of a likely minimally effective once daily dose of approximately 40 mg, assuming 58% bioavailability. Following single administration of 1, 3 and 10 mg of GSK3640254 in this study, a pharmacokinetic model was fit through the concentration-time data and these population PK parameters were used along with the previously assumed PK variabilities. The updated minimally effective once daily dose was approximately 70 mg. At this dose, the mean repeat-dose C_{max} is predicted to be approximately 0.544 µg/mL, mean trough concentration is predicted to be approximately 0.238 µg/mL and mean AUC is predicted to be approximately 8.91 µg.h/mL (Table 8). The anticipated steady-state mean AUC is 2.52-fold lower than the NOAEL in the rat, 6.86-fold lower than the LOAEL in the rat, and 8.23-fold lower than the LOAEL in the dog. The population PK model was further updated with all the concentration-time data available up to 9 May 2018 (excluding the 700 mg SAD dose) and the population PK parameters including the between subject variabilities were used to provide the updated minimally effective once daily dose of approximately 80 mg.

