## 2.3. Study Design

Overview of Study Design and Key Features	

The diagram illustrates the study design. Part 1 (SAD) consists of two cohorts, Cohort 1 and Cohort 2, each with four periods of treatment. Cohort 1 doses are 1 mg, 10 mg, 100 mg, and 400 mg. Cohort 2 doses are 3 mg, 30 mg, 200 mg, and 700 mg. Part 2 (MAD) consists of five cohorts: Cohort 3 (50 mg QD), Cohort 4 (100 mg QD), Cohort 5 (200 mg QD), Cohort 6 (320 mg QD), and an Expansion Cohort (200 mg QD). All cohorts in Part 2 have 14 days of treatment and n=8 participants (A/P=6/2), except for the Expansion Cohort which has n=24 (A/P=18/6).
	
Design Features	
 
Two part, Phase 1, double-blind (sponsor-unblinded), randomized, placebo controlled, single- and repeat-dose escalation study.
 
 
Part 1 (SAD):
 
 
SAD portion will be conducted in an interlocking fashion with 2 separate cohorts of 8 healthy participants each. Each of these 2 cohorts will contain up to 4 escalating doses of GSK3640254.
 
In each escalating period and Cohort, 6 participants will be randomized to GSK3640254 and 2 participants will be randomized to placebo.
 
Participants in Cohort 1 and Cohort 2 will follow the same randomization strategy with alternating ascending doses with 4-period crossover, placebo-controlled.
 
 
Part 2 (MAD):
 
 
Part 2 consists of 4 ascending repeat-dose cohorts (Cohorts 3 to 6), each with 8 participants (active/PBO=6/2) who will receive a once-daily dose of GSK3640254 or PBO for 14 days.
 
Part 2 also includes an Expansion Cohort which will be conducted at the conclusion of cohort 5.
 
The Expansion Cohort will evaluate the rate of GI intolerability in 24 participants (active/PBO =18/6).
 

Dosing	
Part 1 (SAD):
 
 
The dose for Part 1 Cohort 1 of this study were 1 mg for Period 1, 10 mg for Period 2, 100 mg for Period 3 and 400 mg for Period 4.
 
The dose for Part 1 Cohort 2 of this study will be 3 mg for Period 1, 30 mg for Period 2, 200 mg for Period 3 and 700 mg for Period 4.
 
 
Part 2 (MAD):
 
 
The dose for Part 2 of this study were 50 mg for Cohort 3, 100 mg for Cohort 4, 200 mg for Cohort 5 and the expansion cohort, and 320 mg for cohort 6.
 

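### Part 1 dose proportionality rests on one slope over 1–700 mg, with no criterion for triggering the dose-by-dose analysis and no lack-of-fit check

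*SAP*

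**What the plan says.** SAP 8.1.4.1 fits a power model to Part 1: "For Part 1, a power model with subject as the random effect will be fitted". On the interval it says: "The mean slope will be estimated from the power model and the corresponding 90% confidence interval calculated". Proportionality corresponds to a slope of 1, but no acceptance range or decision rule is given.

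The next subsection says a pairwise ANOVA on dose-normalised values, with 3 mg as reference, may be done "if power model does not show dose proportionality". Its example code has treatment as the only term, with no participant effect, although Part 1 is a crossover. SAP 11.12.7 lists that ANOVA for Part 1 as Table 4.5 with no condition, and SAP 11.12.11 lists its SAS output as Listing 86.

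Protocol 3.2.2 describes single-dose Cmax and AUC as rising "in a close to dose proportional manner from 1 to 400 mg with a plateauing in exposure at the 700 mg dose". Protocol 5.5.2 states that the population PK update was made "excluding the 700 mg SAD dose".

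**The concern.** A departure at the top of a 700-fold dose range has little leverage on a slope fitted across the whole range. If the slope interval still includes 1, the text lets the team stop there. If it excludes 1, the slope describes a slight shortfall at every dose, not a levelling-off after 400 mg. Because the trigger is undefined, whether the dose-by-dose estimates are produced is open to choice after the data are seen.

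Dose proportionality is a secondary objective. The plateau is also the protocol's stated reason (5.1) for letting the highest repeat dose reach Cmax values above those seen in the single-dose part. The formal analysis ought to be able to estimate that feature.

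**Working it through.** The documents give no power or miss rate for this analysis, so there is no planned figure to reproduce.

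**Inputs.**
- Cohort 1 received "1 mg for Period 1, 10 mg for Period 2, 100 mg for Period 3 and 400 mg for Period 4".
- Cohort 2 received "3 mg for Period 1, 30 mg for Period 2, 200 mg for Period 3 and 700 mg for Period 4".
- Allocation: "In each escalating period and Cohort, 6 participants will be randomized to GSK3640254 and 2 participants will be randomized to placebo". This gives 8 doses × 6 = 48 active observations from 16 participants, three each.
- Geometric means and CVs come from Protocol Table 3. Log-scale variance is ln(1 + CV²).

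**1. How far a plateau moves the slope.** For the eight log doses the mean is 3.656 and the sum of squares about it is Sxx = 39.24. If exposure is proportional to 400 mg and flat to 700 mg, the last log value falls by ln(700/400) = 0.560. The least-squares slope changes by (6.551 − 3.656) × (−0.560)/39.24 = −0.041, giving 0.959. Simulation of the random-intercept model gives about 0.96 (AUC(0-inf) over 3–700 mg: about 0.94).

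**2. Set against the interval width.** The mean of ln(1 + CV²) over the eight Cmax CVs is 0.142, an SD of 0.377. With no participant effect the slope SE is 0.377/√(6 × 39.24) = 0.0246, and the 90% half-width is 1.684 × 0.0246 = 0.041. Shift and half-width are equal, so detection is close to a coin toss. If more of the variance lies between participants, the slope is more precise and the plateau is detected more often.

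**3. Simulated chance that the 90% CI includes 1 under a complete 400–700 mg plateau.** The layout follows the SAP sequences, with 5,000–6,000 trials per setting, REML, and approximate degrees of freedom. CV pairs are those of Protocol 10.3.3. With true proportionality the CI included 1 in 89.6% of trials, as it should.

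| CVw/CVb (%) | Cmax | AUC(0-inf), 3–700 mg |
|---|---|---|
| 7.5/15 | 0.3% | 0% |
| 12.5/25 | 9% | 2% |
| 15/15 | 12% | 5% |
| 17.5/35 | 25% | 11% |
| 25/25 | 42% | 29% |
| 25/50 | 45% | 30% |
| 35/35 | 59% | 49% |
| 50/50 | 73% | 65% |

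Repeat runs agree to a point or two (41% at 25/25, 59% at 35/35). At 12.5/25 the Cmax figure is nearer 6% if the variance ratio is treated as known.

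Holding total variance at the Table 3 level and raising the within-participant share through 10, 25, 50, 75 and 100% gives 9, 30, 47, 54 and 56% for Cmax, and 2, 19, 39, 51 and 57% for AUC.

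**4. This trial's preliminary means.** Least-squares slopes on Table 3 are:
- Cmax: 0.926 over 1–700 mg (approximate 90% CI 0.926 ± 0.041, or 0.885–0.967) and 0.952 over 1–400 mg.
- AUC: 0.902 over 3–700 mg (0.844–0.959) and 0.940 over 3–400 mg.

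Both full-range intervals exclude 1. A slope of 0.926 means 2^(−0.074) = 0.95, or 5% less than proportional per doubling. It predicts that Cmax rises by a factor 1.75^0.926 = 1.68 from 400 to 700 mg. Table 3 shows 1760.8/1881 = 0.94.

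**5. What a direct contrast gives.** Dose-normalised 700 vs 400 mg Cmax is 0.936/1.75 = 0.53. Treated as two groups of six, the SE is 0.377 × √(2/6) = 0.217, and the 90% CI multiplies and divides by exp(1.684 × 0.217) = 1.44, giving 0.37–0.77. The same calculation for 700 vs 200 mg gives 3.04/3.5 = 0.87 (0.60–1.25), because 200 mg ran low.

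**The case against.** The strongest reply is that the plan does look dose by dose without waiting for the slope. Tables 4.2 and 4.3 summarise PK parameters by treatment, Cmax/Dose and AUC/Dose are derived, dose-normalised individual and box plots are planned, and Table 4.5 carries no condition. This stands. A reader might infer that doses are examined separately only if the slope fails; the SAP does not support that.

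A reader might also infer that the plan would miss a complete plateau in some 40–65% of trials. That range arises for Cmax at CVw = CVb of 25–40% under the CI-includes-1 rule. The SAP states no such rule. Under an equivalence reading (CI inside limits corresponding to an assumed 0.80–1.25 ratio across the range), a false finding of proportionality occurs in under 1% of trials. The documents give no within/between split, and the upper settings exceed the observed spread: 35/35 implies a total variance of 2 × ln(1.1225) = 0.231, against 0.142 from Table 3.

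The preliminary data also point to the trigger firing. With Table 3 means as truth, the CI includes 1 in about 0–14% of trials at the Table 3 total variance, and in up to about 23% at higher CVs. The 320 mg allowance was argued from by-dose means, not from this model, and SAP 2.4 plans no formal test.

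What survives is that the summaries and plots give no model-based ratio with an interval at the top of the range, that the ANOVA text and Table 4.5 disagree, and that one slope cannot describe a plateau even when its interval excludes 1.

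**Conclusion.** The point holds as a gap in specification and a weakness in the summary measure. The trigger is undefined, lack of fit is not checked, and the text conflicts with the list of displays. The chance that a 400–700 mg plateau passes for Cmax runs from near 0% to about 70%, governed mainly by within-participant CV. It rests on three assumptions: the CI-includes-1 rule, exact proportionality up to 400 mg, and log-normal errors. It is not a single miss rate for this trial.

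On the preliminary means the likelier outcome is that the ANOVA is triggered, and the remaining harm is misdescription: a slope near 0.93 read as mild sub-proportionality throughout. The intervals from Table 3 are approximate and ignore the participant effect. The consequence is for reporting a secondary objective; nothing here bears on the primary safety analysis.

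**What to change.** For Part 1:
- Run the dose-as-factor analysis whatever the power model shows, with the same random participant intercept, and extend the example code to all eight doses.
- Report dose-normalised ratios with 90% CIs for 700 vs 400 mg as well as each dose vs the 3 mg reference.
- Report the slope with 90% CI for 1–700 mg and for 1–400 mg.
- Make the ANOVA text agree with Table 4.5.

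The 700 vs 400 mg contrast is the one to add. With Table 3 means as truth it detects the departure in about 66–99% of simulated trials, against about 15–56% for 700 vs 200 mg and 17–53% for a quadratic log-dose term.

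The cost is a few lines of SAS and one extra table panel, with no effect on conduct. The limitation to state is that 400 mg was given only in Cohort 1 and 700 mg only in Cohort 2. The contrast is therefore between participants, its interval is wide, and it carries any difference between the cohorts.
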